5.1 Informed Consent and Assent

- **Delivery:** Information sheets are digitized into screen-reader compatible audio/HTML structures.
- **Execution:** Prior to baseline trials, participants sign a written or authenticated digital biometric thumbprint informed consent form. The document clearly communicates study risks, the right to exit, and explicit consent for capturing research photos with strict facial blurring protocols enforced for future academic dissemination.

5.2 Safety and Trial Discontinuation Protocols

- **Physical Setup:** The indoor virtual reality training environment is surrounded by padded handrails and supervised by an absolute close-proximity manual spotter.
- **Discontinuation Triggers:** Any instance of acute vertigo, simulator-lag sickness, performance anxiety panic, or physical trip event results in an immediate freeze of the system. The hardware is removed, and the participant is placed in a restorative recovery lounge. If symptoms persist beyond 10 minutes, the university on-call clinician or the Saudi Red Crescent ([name]) is alerted.

6. Data Management and Statistical Analysis

6.1 Assessment Instruments

- **Primary Metrics (System Telemetry):** Digital records capturing Time-to-Task Completion (**TTC**), Real-world Collision Rate (**RCR**), and Path Deviation Index (**PDI**).
- **Secondary Metrics (Psychometrics):** Post-trial deployment of a validated 5-point Likert Scale Technology Acceptance Model (TAM) instrument tracking perceived usefulness and ease of use.

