RESEARCH TRIAL PROTOCOL

Title: A Digital Twin Smart Educational Platform for Simulating Physical Obstacles and Safe Navigation Training for the Visually Impaired

Principal Investigator: [[name]]

Affiliation: [King Salman center for Disability Research]

Trial Sponsor/Approval Body: Directorate of Special Education, Ministry of Education,
Jeddah, Saudi Arabia.

IRB Approval Reference: JED-SE-2026-ETH-096

Protocol Version & Date: 1.2

1. General Information

- **Protocol Title:** A Digital Twin Smart Educational Platform for Simulating Physical Obstacles and Safe Navigation Training for the Visually Impaired
- **Principal Investigator:** [[name]]
- **Affiliation:** [King Salman center for Disability Research]
- **Trial Sponsor/Approval Body:** Directorate of Special Education, Ministry of Education, Jeddah, Saudi Arabia.
- **IRB Approval Reference:** JED-SE-2026-ETH-096
- **Trial Registration Identifier:**
- **Protocol Version & Date:** Version 1.2 – June 2026.

2. Project Summary and Objectives

The purpose of this clinical/educational trial is to evaluate the spatial orientation and mobility (O&M) efficacy of a dynamic non-invasive digital rehabilitation prototype. The platform bridges high-fidelity urban engineering modeling with adaptive instructional scaffolding to accelerate independent walking safety for visually impaired people (VIP).

Primary Objectives:

- To evaluate if adaptive virtual twin training lowers physical contact failure events during outdoor real-world urban navigation.
- To benchmark the execution latency of multi-modal binaural sound rendering and vibrotactile hardware actuators.
- To document behavioral technology acceptance vectors (TAM) across the target demographic group.

3. Study Design and Methodology

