6.2 Analysis Plan

- **Data Integrity:** Data anonymization is achieved via alphanumeric key mapping (e.g., VIP_JED_01). Missing data points will be addressed using multiple imputation mechanisms.
- **Hypothesis Testing:** Group mean differences will be verified using an Independent Samples (t)-test. Longitudinal skill growth across the 10 sessions will be tracked via a Two-Way Repeated Measures Analysis of Variance (**ANOVA**), setting statistical significance thresholds at an absolute value of ($\alpha = 0.05$). All calculations will run natively within SPSS or Python scipy libraries.

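### Three unranked primary metrics share one undivided 0.05 threshold while the only efficacy objective concerns collisions; if success on any one metric counts, the false-positive risk is up to 14.3%

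*Protocol*

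**What the plan says.** Section 6.1 of the protocol puts three outcomes under one primary label: "Digital records capturing Time-to-Task Completion (TTC), Real-world Collision Rate (RCR), and Path Deviation Index (PDI"). It gives no order among them and does not say whether success needs one of them or all of them. The secondary label in the same section covers "Post-trial deployment of a validated 5-point Likert Scale Technology Acceptance Model (TAM) instrument".

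Section 6.2 says: "Group mean differences will be verified using an Independent Samples (t)-test". It continues: "Longitudinal skill growth across the 10 sessions will be tracked via a Two-Way Repeated Measures Analysis of Variance", "setting statistical significance thresholds at an absolute value of" 0.05. That is the only significance level in the protocol, and it is not divided.

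Section 2 lists three primary objectives. The first is the only one about efficacy: "To evaluate if adaptive virtual twin training lowers physical contact failure events during outdoor real-world urban navigation". The second is to benchmark the latency of the sound and haptic hardware. The third is: "To document behavioral technology acceptance vectors (TAM) across the target demographic group".

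**The concern.** The objectives and the metric list give different answers to the question of what is primary.

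- The efficacy objective points to RCR only. TTC and PDI are primary metrics that answer no stated objective.
- TAM is primary in section 2 and secondary in section 6.1.
- Latency is primary in section 2 and has no metric in section 6.1.

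With three metrics of equal rank and one threshold, a significant result on any one of them could be presented as the trial's primary success, and the choice could be made after the data are seen. The nominal 0.05 would then not be the error rate of the headline claim.

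**Working it through.** **No figure to reproduce.** The 0.05 is stated, not derived. The protocol gives no overall error rate, power, effect size or standard deviation.

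**Inputs from the protocol.**
- Three primary metrics (section 6.1).
- Threshold 0.05 and an independent-samples t-test (section 6.2).
- 30 participants (section 4) allocated 1:1 (section 3.1), so 30 / 2 = 15 per arm and 28 degrees of freedom.

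**Assumptions, not in the protocol.** Tests are two-sided, each metric is tested at 0.05, there is no true difference on any metric, and the three outcomes share a common correlation within participants. The protocol gives no correlation, so a range is shown.

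**Independent metrics, any one counts.** 1 − 0.95³ = 1 − 0.8574 = 0.1426, or 14.3%.

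**Correlated metrics.** The table comes from a simulation with 15 per arm, normal outcomes, pooled t-tests and 100,000 trials per correlation. The entries at correlation 0, and those at correlation 1, are exact.

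| Correlation | Any one of three significant | All three significant |
|---|---|---|
| 0 | 14.3% | 0.05³ = 0.01% |
| 0.3 | 13.7% | 0.1% |
| 0.5 | 12.5% | 0.3% |
| 0.7 | 11.2% | 0.9% |
| 0.8 | 9.9% | 1.3% |
| 0.9 | 8.5% | 2.2% |
| 1 | 5% | 5% |

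So 11-14% describes an any-one rule with correlations from 0 to about 0.7. Under an all-three rule the rate never exceeds 5%.

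**Favourable direction only.** The first objective asks about a reduction, so one may count only false claims in favour of the new training. For independent metrics this is 1 − 0.975³ = 7.3%. At correlation 0.7 it is 5.6% by simulation. The reference for a single test is 2.5%. The ratio to a single test matches the two-sided case: 7.3 / 2.5 and 14.3 / 5 are both about 2.9, and 5.6 / 2.5 and 11.2 / 5 are both about 2.2.

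**Remedies compared.** A Bonferroni split gives 0.05 / 3 = 0.0167 per metric. The family-wise rate is then 1 − (1 − 0.0167)³ = 4.9% if independent, 4.3% at correlation 0.5 and 4.0% at 0.7. With 15 per arm, the difference detectable with 80% power rises from 1.06 SD at 0.05 to 1.25 SD at 0.0167. One named primary endpoint holds the headline error at 5% and keeps the 1.06 SD.

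**TAM and latency.** These mismatches need no arithmetic. Setting section 2 beside section 6.1 shows them, and they do not enter any of the rates above.

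**The case against.** **A multiplicity method may sit in the SAP.** The SAP is not at hand, and an adjustment, a testing order or a success rule is often placed there. This stands: the absence of an adjustment method is not the finding. The choice of primary endpoint, however, belongs in the protocol. The protocol makes that choice in two places that disagree, and an SAP cannot cure this without a protocol amendment.

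**Testing each metric at 0.05 is an inference.** Section 6.2 does not say which metrics the t-test covers, and grammatically the threshold is attached to the ANOVA sentence. This also stands. One undivided threshold applied to each primary metric is the natural reading, but it is not written out.

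**Stronger readings that a reader might infer.**
- *That the trial's false-positive rate simply is 11-14%.* The protocol states no any-one rule, no sidedness and no correlation, so the figure is conditional. An all-three rule would give no inflation.
- *That the ANOVA doubles the number of primary tests and raises the rate further.* Section 6.2 says only that skill growth over sessions will be tracked. It neither makes this a primary test nor applies it to every metric. RCR is a real-world measure, while the experimental sessions take place in a lab frame (section 4.1), so a session-by-session ANOVA of RCR is not evident.
- *That the TAM mismatch contributes to the error rate.* The rates come from the three telemetry metrics alone. TAM is to be documented and latency benchmarked. Both verbs are descriptive, and neither clearly adds a hypothesis test.

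**RCR alone is not the only solution.** A stated order, an alpha split or an all-three rule would also control the error. This is correct. RCR is preferred because the protocol's own first objective points to it and because it costs no alpha in a trial of 15 per arm.

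**Conclusion.** The point holds in a conditional form. The protocol fixes three unranked primary metrics and one undivided threshold, while its only efficacy objective matches one of the three. If any one metric suffices, the two-sided chance of at least one false-positive primary result is up to 14.3%, on the assumptions listed in the working. An all-three rule would remove the inflation, but the protocol does not state that rule either.

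The conflicting status of TAM and the missing metric for latency are separate contradictions within the protocol. They are certain on the text and carry no figure.

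**What to change.** Amend sections 2, 6.1 and 6.2 before any outcome data are seen by arm:

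1. Name RCR at the post-intervention field assessment as the single primary endpoint, compared between arms once at two-sided 0.05.
2. Make TTC and PDI secondary. Test them only if RCR is significant, either in a stated fixed order at 0.05 each or by Holm (smaller p-value against 0.05 / 2 = 0.025, then the other against 0.05).
3. Label the session-wise ANOVA as supportive or exploratory.
4. Make TAM secondary in section 2 so that it agrees with section 6.1.
5. List latency as a descriptive technical result, outside the hypothesis tests.

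If the sponsor wants to keep three primary metrics, the protocol should state an order, an alpha split or an all-three rule. An equal split has the power cost shown in the working.

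The change costs wording only, with no extra participants or data. The downside is that TTC and PDI can no longer support stand-alone primary claims.

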6.2 Analysis Plan

- **Data Integrity:** Data anonymization is achieved via alphanumeric key mapping (e.g., VIP_JED_01). Missing data points will be addressed using multiple imputation mechanisms.
- **Hypothesis Testing:** Group mean differences will be verified using an Independent Samples (t)-test. Longitudinal skill growth across the 10 sessions will be tracked via a Two-Way Repeated Measures Analysis of Variance (**ANOVA**), setting statistical significance thresholds at an absolute value of ($\alpha = 0.05$). All calculations will run natively within SPSS or Python scipy libraries.

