3.1 Trial Design

- **Structure:** A prospective, single-blind, randomized, two-arm parallel interventional controlled study.
- **Allocation Ratio:** (1:1) balanced random partition into an Experimental Arm and a Active Control Arm.
- **Blinding:** Single-blind. Participants are unaware of which training methodology is classified as the novel paradigm. Double-blind execution is implemented during post-intervention field score assessments via independent evaluation observers.

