3.2 Participant Recruitment and Selection

- **Recruitment Channel:** Institutional databases through partnership networks at the Directorate of Special Education and local blind associations in Jeddah.

Inclusion Criteria:

[figure not shown]
- Adults aged between 18 and 60 years old legally diagnosed with severe visual impairment or total blindness.
- Ability to walk unassisted for a minimum continuous duration of 15 minutes.
- Proficiency in screen-reader accessibility controls on smartphone user interfaces.

Exclusion Criteria:

- Co-occurring profound sensorineural hearing loss (preventing 3D spatial binaural discrimination).
- Active upper/lower-limb motor neuropathies disrupting haptic micro-actuator detection.
- Diagnosed vestibular syndromes or severe motion sickness history.

4. Intervention and Execution Plan

[Recruited Sample: N = 30 VIP]

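### The between-arm t-test on 15 per arm makes no use of the baseline trials; if those trials record the outcome metrics, adjusting for them would probably gain power

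*Protocol*

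**What the plan says.** Section 6.2 gives one test for comparing the arms: "Group mean differences will be verified using an Independent Samples (t)-test". It names no covariate, change score or baseline term. The significance level appears in the same section ("setting statistical significance thresholds at an absolute value of ($\alpha = 0.05"), without saying whether tests are one- or two-sided.

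The only other model is for the training period: "Longitudinal skill growth across the 10 sessions will be tracked via a Two-Way Repeated Measures Analysis of Variance". It describes learning over the sessions and does not adjust the comparison of post-intervention outcomes for a starting value.

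The outcomes in section 6.1 are "Digital records capturing Time-to-Task Completion (TTC), Real-world Collision Rate (RCR), and Path Deviation Index (PDI", given without measurement times. Baseline trials appear once, in section 5.1: "Prior to baseline trials, participants sign a written or authenticated digital biometric thumbprint informed consent form". What they record is not stated.

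The size comes from the line under heading 4, "Recruited Sample: N = 30 VIP", and the allocation from section 3.1, "1:1) balanced random partition into an Experimental Arm and a Active Control Arm". No effect size, SD, target power or sample-size calculation is given.

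**The concern.** A two-sample t-test leaves all between-person variation in its error term. Section 3.2 admits adults from 18 to 60 with either severe impairment or total blindness, so wide differences in starting navigation performance are plausible. Section 3.1 describes no stratification that would even them out.

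If a participant's baseline result predicts the post-intervention result, part of that variation can be removed by adjustment without recruiting anyone. With 15 per arm this matters, because the unadjusted test reaches 80% power only for a difference of about 1.06 SD. What is at stake is the chance of missing a real effect, and the width of the confidence interval. The validity of the test is not in question.

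**Working it through.** There is no stated power figure to reproduce, so the check compares the named test with a baseline-adjusted one at the planned size.

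**Inputs from the protocol**
- N = 30 (heading 4) at 1:1 (section 3.1), so n = 30/2 = 15 per arm.
- Alpha 0.05 (section 6.2).

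**Assumed, because the protocol gives no figure**
- Two-sided testing.
- All 30 analysed. No dropout rate is stated; for missing values the plan says only "Missing data points will be addressed using multiple imputation mechanisms".
- A true difference of d = 0.8 SD.
- Baseline-outcome correlation ρ from 0 to 0.7.
- Approximately normal outcomes.

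**Unadjusted t-test**
- Variance of the difference in SD units: 2/n = 2/15 = 0.1333, so SE = 0.365.
- Noncentrality: 0.8/0.365 = 2.19. With 28 df the critical value is 2.048.
- Power from the noncentral t: **56.2%**. At d = 0.5 it is 26.2%, and at d = 1.0 it is 75.3%.
- Difference detectable with 80% power: **1.06 SD**.

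**ANCOVA with one baseline covariate**
- Variance: (2/n) × (1 − ρ²) × (1 + 1/26). The last factor is the average price of chance baseline imbalance, with 2n − 4 = 26. There are 27 df and the critical value is 2.052.
- Example at ρ = 0.5: 0.1333 × 0.75 × 1.0385 = 0.1038, SE = 0.322, noncentrality 0.8/0.322 = 2.48, power 66.8%.

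| Assumed ρ | ANCOVA power at d = 0.8 | Change from 56.2% (points) | Detectable at 80% power (SD) |
|---|---|---|---|
| 0 | 54.5% | −1.7 | 1.08 |
| 0.2 | 56.2% | 0 | 1.06 |
| 0.3 | 58.4% | +2.2 | 1.03 |
| 0.5 | 66.8% | +10.6 | 0.94 |
| 0.7 | 82.7% | +26.5 | 0.77 |

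**Simulation check.** With 20,000 trials per setting, ANCOVA power at d = 0.8 was 54.4%, 58.8%, 66.8% and 83.2% at ρ = 0, 0.3, 0.5 and 0.7, against about 56% for the t-test. Under no effect, both tests rejected in about 5% of trials.

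**Equivalent sample size, from variance reduction alone.** N/(1 − ρ²) gives 30/0.75 = 40 unadjusted participants at ρ = 0.5, and 30/0.51 ≈ 59 at ρ = 0.7.

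**Change scores as an alternative.** A t-test on change has variance factor 2(1 − ρ). At ρ = 0.5 this equals 1, so power is again 56.2%. At ρ = 0.3 it falls to 43.2%.

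**The case against.** The strongest objection is that the information may not exist. Baseline trials are mentioned once, in the consent section. Section 6.1 attaches no time points to the metrics. RCR is a real-world rate, and the first objective in section 2 concerns outdoor navigation, so an indoor baseline session need not yield it. This stands, and it makes the point conditional on what is recorded.

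A second objection is that the gain is not guaranteed. It also stands. At ρ = 0 adjustment costs 1.7 points, break-even is near 0.2, and the protocol gives no correlation. RCR is a rate rather than a normal variable, so the table is only a guide for it.

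A third is that randomisation already makes the t-test unbiased, with correct type I error. A reader might infer from the small arms that chance imbalance biases the result or invalidates the test. The protocol does not support that, because such imbalance is already reflected in the t-test's standard error. What remains is imprecision in the single trial that is run: the standardised baseline difference has SD √(2/15) = 0.37, so it exceeds 0.5 SD in about 17% of randomisations (normal approximation).

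A last objection is that covariates are often left to an analysis plan, which may exist unseen, and that the sentence in 6.2 is generic enough to allow change scores. But the protocol is not silent. It names a test that takes no covariate, so an analysis plan adding one would depart from it. Change scores gain nothing at ρ = 0.5 and lose power below that.

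**Conclusion.** The point holds as a conditional loss of efficiency. Section 6.2 fixes an unadjusted t-test with 15 per arm, and no part of the analysis uses the baseline trials. To the extent that those trials record TTC, RCR or PDI, that information is left unused. At d = 0.8 the cost is about 11 points of power if ρ is 0.5 and about 26 points if ρ is 0.7. It is negligible at 0.2 and slightly negative at 0.

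Confidence is high that the planned analysis ignores baseline, and medium on the size of the gain. The size rests on assumed values for ρ, d, sidedness and complete data, and on normal outcomes.

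A reader might also infer that all three outcomes are certainly measured at baseline, or that adjustment is bound to shrink the standard error. The protocol establishes neither.

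**What to change.** 1. State in section 6.1 which of TTC, RCR and PDI the baseline trials record.
2. In section 6.2, for each metric recorded at baseline, replace the t-test with ANCOVA of the post-intervention value on randomised arm and the baseline value of the same metric. Report the adjusted difference with a 95% CI.
3. Keep the unadjusted t-test as a sensitivity analysis. It remains the main comparison for any metric not recorded at baseline.
4. Settle this before outcome data are seen, so that the choice to adjust cannot depend on the result.

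The cost is a sentence or two of text, one degree of freedom (27 in place of 28), and up to about 2 points of power if baseline proves unrelated to outcome. SPSS, already named in section 6.2, can fit the model. No additional baseline walk or participant is required.

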4.1 The Experimental Arm (AMRLE Group)

Participants assignment code: Adaptive Multi-modal Reality Learning Environment (**AMRLE**).

- **Regimen:** 10 sessions distributed over 5 consecutive weeks (2 sessions per week). Each session lasts 25 minutes.
- **Environment:** Trainees walk inside a safe lab tracking frame wearing open-ear headphones and a custom Bluetooth-enabled 4-zone haptic belt.
- **Execution:** The backend logic tracks user location via an Octree spatial partition mesh. The AI updates environmental complexity (C_{t+1}) using real-time collision loops. The layout dynamically spawns physical blockades (e.g., Jeddah sidewalk construction gaps, unexpected street bins), forcing cognitive adjustments.

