4.2 The Control Arm (Conventional Technology Group)

- **Regimen:** 10 sessions over 5 weeks (2 sessions per week, 25 minutes per session).
- **Environment:** Traditional indoor/outdoor spatial orientation tracks.

- **Execution:** Trainees receive conventional manual orientation and mobility (O&M) rehabilitation. This includes walking on fixed paths using standard white canes, combined with verbal description spatial audio scripts and layout orientation blueprints. No adaptive virtual elements are utilized.

5. Ethical Considerations and Safety Monitoring

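### The ten-session ANOVA, read as arm by session, mixes skill change with a difficulty change that occurs in the AMRLE arm only, so its result cannot be attributed to skill

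*Protocol*

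**What the plan says.** Under its hypothesis-testing item, Protocol section 6.2 gives two analyses. One is an independent-samples t-test for group mean differences. The other concerns the training period: "Longitudinal skill growth across the 10 sessions will be tracked via a Two-Way Repeated Measures Analysis of Variance", with significance at 0.05. It does not name the outcome or the two factors of the ANOVA.

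The sessions differ by arm:

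- **AMRLE arm (4.1).** "Trainees walk inside a safe lab tracking frame wearing open-ear headphones". Difficulty responds to performance: "The AI updates environmental complexity (C_{t+1}) using real-time collision loops". Obstacles change as well: "The layout dynamically spawns physical blockades".
- **Control arm (4.2).** The setting is described as "Traditional indoor/outdoor spatial orientation tracks". On content: "This includes walking on fixed paths using standard white canes". On adaptation: "No adaptive virtual elements are utilized".

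Section 6.1 lists time to completion, real-world collision rate and path deviation as the primary metrics. It states no adjustment for difficulty. The only assessment described outside the training sessions and scored by independent observers is the post-intervention field assessment in 3.1.

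**The concern.** Section 6.2 has already fixed what the ANOVA is meant to show, namely growth in skill. In a two-arm trial with session as one factor, arm is the obvious second factor, and the arm-by-session term would be the test of whether one training builds skill faster.

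That reading needs session scores in the two arms to be on one scale. They are not. In AMRLE, the difficulty met in a session depends on the trainee's earlier collisions. In control, nothing in the protocol makes difficulty depend on performance. An improving AMRLE trainee may meet a harder layout and show flat collision counts, while a control trainee may improve partly by learning a path. Randomisation does not protect against this, because the distortion is produced by the intervention after allocation.

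At stake is a planned p-value that would be reported as evidence on comparative skill growth when it also reflects how strongly the software adapts.

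**Working it through.** **1. What the contrast estimates.** On a log or logit scale, let the session score be S(t) + D(t), where S is the part due to skill and D the part due to task difficulty. The between-arm difference in change is

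[ΔS(AMRLE) − ΔS(control)] + [ΔD(AMRLE) − ΔD(control)].

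On the fixed paths ΔD(control) is 0. By 4.1, ΔD(AMRLE) is not, and it depends on earlier scores. Only the first bracket is skill.

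**2. Inputs.** From the protocol: N = 30 and 1:1 allocation, so 30/2 = 15 per arm; 10 sessions; α = 0.05. There is no stated power, collision rate or adaptation rule, so there is no figure of the plan to reproduce. Everything below on skill, collisions and adaptation is assumed, including that difficulty rises when collisions fall.

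**3. Collision proportion at session 10.** Assume 20 obstacles, a 31% start (logit −0.800), skill gain of 0.30 logit per session in AMRLE and 0.15 in control, and a 30% target (logit T = −0.847).

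No adaptation, for an average trainee:
- AMRLE: −0.800 − 9 × 0.30 = −3.500, or 2.9%.
- Control: −0.800 − 9 × 0.15 = −2.150, or 10.4%.

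Now let AMRLE difficulty close a fraction f of the logit gap to target after each session. Then L(t+1) = L(t) − 0.30 + f[T − L(t)]. The limit is L* = T − 0.30/f, and L(10) = L* + (1 − f)^9 [L(1) − L*].
- f = 0.1: L* = −3.847; L(10) = −3.847 + 0.387 × 3.047 = −2.667, or 6.5%.
- f = 0.2: L* = −2.347; L(10) = −2.347 + 0.134 × 1.547 = −2.140, or 10.5%, which is parity with control.
- f = 0.4: L* = −1.597; L(10) = −1.597 + 0.010 × 0.797 = −1.589, or 17%.

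Simulation with binomial counts and variation between people (SD 0.3 to 0.5 logit) gives the same picture. Control ends at about 11% throughout.

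| Assumed AMRLE adaptation | AMRLE, session 10 |
|---|---|
| None | 3% |
| 0.4 × (0.30 − observed proportion) | 4.8% |
| 0.4-logit steps, capped at +0.8 | 6.6% |
| 0.4-logit steps, capped at +1.2 | 9.3% |
| 0.2-logit steps, or 0.2 of the gap | 10-11% |
| 0.4 of the gap | 17.5% |
| 0.4-logit steps, no cap | 18.5% |

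**4. Behaviour of the test.** A second model uses Poisson collisions (base rate 8 per session, between-person log-SD 0.3). Skill lowers the log rate by g per session. AMRLE log difficulty moves by k × log(8/(collisions + 0.5)) after each session. The arm-by-session F test has 10 − 1 = 9 and (30 − 2) × 9 = 252 degrees of freedom; there were 2,000 replicates per scenario.

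| | k = 0 | k = 0.1 | k = 0.25 | k = 0.5 |
|---|---|---|---|---|
| Equal growth (0.10 in both): rejects | 4.8% | 11.1% | 36.1% | 69.2% |
| AMRLE better (0.15 vs 0.10): slope favours control | 13% | 53% | 94.5% | 100% |
| Same: significant, slope favours control | 0.6% | 3.5% | 20.9% | 61.3% |
| AMRLE doubled (0.20 vs 0.10): slope favours control | 3% | 26% | 83% | 99.8% |

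In the 0.15 against 0.10 case the true session-10 collision ratio at equal difficulty is exp(−9 × 0.05) = 0.64 in favour of AMRLE. With equal growth and k of 0.25 or more, practically all rejections favour control. If neither arm learns, rejection stays near 5% at k = 0, 0.25 and 0.5.

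**The case against.** The strongest reply is that the criticised test is not written down. Section 6.2 names no outcome, no factors and no interaction, and such detail commonly sits in an SAP, which may exist. An SAP could choose a common test task or the complexity level as the outcome without contradicting 6.2. This stands as a limit: the point applies to a between-arm comparison of raw session metrics. That remains the natural reading, because the sentence is part of hypothesis testing in a two-arm trial, and the protocol describes no per-session task shared by the arms.

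Four other limits also stand:

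- The adaptation rule is unknown. Section 4.1 says that complexity is updated, without direction, step, target or ceiling. A reader might infer that the faster-learning arm will look worse. The documents do not support that: under weak or capped rules it still looks better, only by less.
- Control training *includes* fixed paths. It need not consist of them alone, so completely constant difficulty in that arm is a simplification.
- The collision metric in 6.1 is a real-world rate and may not be recorded in lab sessions. A ten-session analysis must still use session data, and time and path deviation also depend on difficulty.
- A reader might infer that the trial's main comparison is compromised. It is not. The first objective in section 2 concerns outdoor navigation, and a t-test on field scores taken after the intervention does not pass through the adaptive sessions.

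**Conclusion.** The concern holds for the session-level ANOVA and no further. Whatever the adaptation rule, an arm-by-session comparison of raw metrics adds a difficulty change in one arm to the skill contrast. Its result, significant or not, cannot be attributed to skill.

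Distortion is expected wherever difficulty shifts over sessions; reversal is conditional. On the assumptions shown, a true 3% against 11% advantage becomes 5-7% against 11% under weak or tightly capped adaptation, parity at about 0.2 (logit step or fraction of the gap), and about 18% against 11% at 0.4. These figures illustrate a range and do not predict this system.

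It would go too far to say that the interaction carries no information at all. It reflects skill and difficulty together, and the plan gives no means of separating them. This should be fixed, preferably before sessions begin, but it does not threaten the post-intervention between-arm comparison.

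**What to change.** In section 6.2:

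1. Remove the between-arm session ANOVA from hypothesis testing.
2. State that between-arm inference comes from the masked post-intervention field assessment in 3.1, using the same task in both arms. Adjust for baseline if the baseline trials mentioned in 5.1 include that task; the protocol does not say whether they do.
3. Report session data within each arm, descriptively. Show AMRLE results alongside the complexity level C_t if it is recorded. Section 4.1 implies that the system holds this value, but 6.1 does not list it among the recorded data.

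The cost is a rewording of 6.2 and the loss of one planned p-value.

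If a between-arm growth comparison is wanted, the alternative is an identical non-adaptive test task for both arms at set sessions, with the ANOVA run on that. This adds assessments and is more than a rewording. It must be decided before training starts, because a common task cannot be added to sessions already run.
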